TITLE OF STUDY:

Sexual and vaginal health in breast cancer women receiving aromatase inhibitors before and after CO2 laser therapy: a randomized, double-blind, sham-controlled trial.

NCT number: Not yet assigned

Document date: 24th August 2020

GLOSSARY:

BCS: Breast cancer survivors

AI: Aromatase inhibitors

GSM: Genitourinary syndrome of menopause

PLISSIT Model: Permission, Limited information, Specific suggestions, intensive therapy

FSFI: Female sexual function index

VAS: Visual analogue scale

S-BIS: Spanish- Body image scale

SF-12: Short form-12 healthy survey

AEs: Adverse events

SAEs: Serious adverse events

SUMMARY (max 300 words):

Please summarise the background, aims, methods and expected impact in simple terms

Background: Vulvovaginal health, directly linked to sexual health, is a key factor for female pleasure. BCS receiving AI are likely to present severe GSM and sexual complaints. Innovative options, as vaginal laser therapy, are emerging to treat GSM and sexual dysfunctions. Nowadays, data in BCS is scarce, moreover, few studies included patients receiving AI [16]. Different meta-analysis [17-23] found GSM [24, 25] and sexual function [9, 10] may improve significantly at short-term, however, the body of evidence is of low quality. Therefore, before recommendation of laser therapy for sexual complaints in BCS with GSM, there are unmet needs to be solved: efficacy and safety at long-term, biases related to patients' expectations and a detailed assessment of the complex underpinnings of sexuality.

Aims: To evaluate sexual and vaginal health in BCS receiving AI with GSM, before and after CO2 laser therapy compared to a sham-controlled group.

Methods: Prospective, randomized, double-blind controlled study with two parallel study arms: 1) Fractional CO2 laser therapy (5monthly sessions). 2) Sham laser therapy (5monthly sessions). After end-treatment, patients are followed up at 1 month and 6 months. BCS treated or undergoing AI with GSM and sexual function impairment, will be suitable. All patients will maintain first-line non-hormonal treatment and sexual assessment (PLISSIT Model) according with usual care. The primary outcome is improvement in sexual function (FSFI total score). As secondary outcomes: resumption sexual activity, sexual activity frequency, dyspareunia (VAS), female sexual dysfunction, sexual dimensions (FSFI), body image (S-BIS), quality of life (SF-12), vaginal pH acidification, maturation index and Vaginal Health Index of Gloria Backmann, adverse events, satisfaction (Likert scale) and adherence to treatment.

Expected impact: Emergent, non-invasive, laser therapy has significant benefit for BCS with AI, improving subjective and objective sexual and vaginal health outcomes and adding value to the usual care multidisciplinary approach.

BACKGROUND (max 500 words):

Sexuality is a central aspect of being human throughout life encompasses sex, gender identities and roles, sexual orientation, eroticism, pleasure, intimacy and reproduction [1]. Most of these aspects may be affected in breast cancer survivors (BCS). In a recent meta-analysis [2, 3] focused on sexual function through Female Sexual Function Index (FSFI) among BCS, female sexual dysfunction prevalence was 73,4% (95 % CI 64–82.8 %, I2 = 96.8 %) and mean FSFI 19.28 (95 % CI 17.39–21.16, I2 = 97.6 %). Several modifiable risk factors for sexual dysfunction in BCS may be optimum targets for intervention: amelioration of vaginal discomfort and urinary incontinence, the benefits of breast conserving surgery on body image or the evaluation of relationship quality [4, 5] Due to the multifaceted nature of the factors affecting sexuality in BCS, most authors [3-10] encouraged the need for comprehensive assessment and for a multidisciplinary approach.

BC diagnosis and/or its treatments (surgery, chemoradiotherapy, hormonal therapy) may altered sexual health. Vulvovaginal health, directly linked to sexual health, is a key factor for female pleasure. Genitourinary syndrome of menopause (GSM) is caused by decline in estrogen at menopause, which may also appear or worsen after systemic cancer treatments as aromatase inhibitors (AI). GSM is associated with sexual symptoms (lack of lubrication, discomfort or pain, impaired function), genital symptoms (dryness, burning, irritation) and urinary symptoms (urgency, dysuria, recurrent urinary tract infections). BCS receiving AI are one of the groups most likely to present severe GSM and sexual complaints [11]. A cross-sectional study [12] on 129 BCS during the first 2 years of adjuvant AI therapy, found 3 out of 4 women were distressed about their sexual problems. Only 52% of women had been sexually active when endocrine therapy began, but 79% of that group developed new sexual problems.

The first line of treatment for GSM is non-hormonal therapy (regular sexual activity, moisturizers-lubricants, pelvic-floor relaxation techniques, dilators) although in many women these options will not adequately control symptoms. Hormonal therapies must be used with caution in women with estrogen-dependent cancers [13-15]. So, alternative options are emerging for this subset of patients, such as vaginal laser therapy. Different studies [16-18] provided short-term data on non-cancer patients that showed laser therapy was feasible, safe and improved objective and subjective GSM. Data regarding sexuality derived from secondary endpoints and suggested that laser therapy may improve sexual function, mainly decreasing sexual pain [16, 18]. To date, data on laser therapy in BCS is scarce, moreover, few studies included patients receiving ongoing AI [19]. The CO2 laser was the most frequently used device. Different reviews and meta-analysis [20-26] found GSM [27, 28] and sexual function [9, 10] may improve significantly at short-term, however, the body of evidence is of low quality. Therefore, before recommendation for the use of laser therapy for sexual complaints in BCS with GSM, there are unmet needs to be solved as efficacy and safety at long-term, biases related to patients' expectations of therapy and a detailed assessment of the complex underpinnings of sexuality.

AIMS (max 200 words):

To answer the unmet needs previously mentioned, the aim of the current study is to verify the outcomes of sexual and vaginal health in breast cancer women receiving AI, who were experiencing symptoms of GSM, before and after CO2 laser therapy compared to a sham-controlled group.

Specifically, we will compare the following subjective and objective measurements of sexual and vaginal health:

MAIN GOAL: Report an improvement in sexuality:

- Primary outcome: sexual function (FSFI total score)

- Secondary sexual outcomes: resumption sexual activity (sexually active vs non-sexually active), sexual activity frequency (n° sexual activity/week), dyspareunia (VAS), female sexual dysfunction (VAS sexual life distress), sexual dimensions: desire, arousal, lubrication, orgasm, satisfaction and pain (FSFI) and body image (S-BIS)

OTHER OBJECTIVES: Report an improvement on GSM symptoms (efficacy) and quality of life, feasibility and safety of laser therapy in BCS:

- Secondary non-sexual outcomes: quality of life (SF-12). Verify an acidification of the vaginal pH, an improvement in the maturation index and an improvement in the Gloria Backmann Index: Vaginal Health Index. To evaluate toxicity associated with vaginal laser therapy in this population (AEs and SAEs). To determine how many women with the defined patient eligibility will complete all treatments.

METHODS (max 500 words):

DESIGN: Prospective, randomized, double-blind controlled study with two parallel study arms: ARM I: Patients undergo fractional CO2 laser therapy at 5 times points 30 days apart. ARM II: Patients undergo sham laser therapy at 5 time points 30 days apart. After completion of the treatment, patients are followed up at 1 month and 6 months.

RANDOMIZATION PROCESS: A randomization list will be generated in multiple blocks of 2 and 1: 1 ratio with STATA version 15.1 or higher.

STUDY SUBJECTS: Patients treated or undergoing AI for BC in the Breast Cancer Unit of the Hospital Clínic and who present symptoms related to GSM that condition their sexual function and quality of life, despite receiving first-line non-hormonal treatment: regular sexual activity (such as mutual and self-touch masturbation, manual or vibrator stimulation, oral sex, sexual intercourse, massage and other forms of physical intimacy), moisturizers, lubricants, pelvic-floor relaxation techniques and/or dilators. Inclusion and exclusion criteria are summarized in Table 1.

STUDY GROUPS: All patients will receive instructions to maintain first-line non-hormonal treatment, as well as sexual assessment using the PLISSIT Model according with usual care in our hospital.

The study group will be treated with a vaginal fractionated CO2 laser protocol (The SMARTXIDE TOUCH (Deka) equipment with an autoclavable vaginal probe following the manufacturer's protocol (Annex 9).

The control group will receive treatment with a sham-CO2 laser using a double-blinded protocol.

STUDY STRUCTURE (See Annex 1).

SAMPLE CALCULATION

Considering FSFI score as the main variable of the study, we performed a calculation of the hypothesis contrast study sample with the comparison of two independent means. Accepting an alpha risk of 0.05 and a beta risk of less than 0.1 in a bilateral contrast, 44 subjects in the first group and 44 in the second. The common standard deviation is assumed to be 1. A follow-up loss rate of 15% has been estimated.

STATISTIC ANALYSIS

Descriptive statistics will be used according to standard calculation methods.

The comparison between the two treatments at the end of the study will be evaluated through the change with the baseline using a mixed repeated measures model (MMRM) adjusted for the baseline value and including the treatment and the time in the model.

The variables of repetitive evaluation over time are analyzed according to the following strategy: (a) continuous variables with a repeated measures mixed longitudinal model (MMRM); (b) binary or non-normal variables with marginal models (Generalized Estimating Equation: GEE). Other variables will be studied as follows: Fisher's exact test for categorical variables, Student's t test for continuous variables between 2 groups. Non-parametric methods for independent data (Mann-Whitney U for 2 groups or Kruskal-Wallis test for more than 2 groups) will be used if necessary. The level of statistical significance will be 5% bilateral. The main analysis will be by Intention to Treat (ITT).

REFERENCES:

1. World Health Organization. Defining sexual health. Report of a technical consultation on sexual health 28-31, January 2002, Geneva. Geneva: World Health Organization, 2006.
2. MI Maiorino, P Chiodini, G Bellastella, D Giugliano, K Exposito. Sexual dysfunction in women with cancer: a systematic review with meta-analysis of studies using the Female Sexual Function Index. *Endocrine* (2016) 54:329–3413.

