CO2 laser equipment: The SMARTXIDE TOUCH provided free of charge by DEKA = 0€

Tablet:

Smartphone and phone line (18 months - study phone contact):

C) Travel Expenses

Dissemination of the results of the study of national / international conferences 1500€

COST CATEGORY	COST
1. Personnel	20.830,6 €
2. Consumables and services	7669,4 €
3. Travel expenses	1.500 €
TOTAL	30.000

SCHEDULE:

	0-1	2-3	4	5	6	7	8	9	10	11-14	15	16	17	18
Database design	■													
Recruitment	■	■												
Baseline visit		■	■											
Treatment			■	■	■	■	■	■						
Follow-up visits								■	■		■	■		
Cytology		■	■					■	■		■	■		
Questionnaires		■	■					■	■		■	■		
Analysis results												■	■	
Manuscript edition													■	■

ATTACHMENTS:

Please attach:

CV of the PI including list of all peer reviewed publications

Copies of ethics and regulatory permissions

Any figures or tables

Table 1: inclusion and exclusion criteria

Inclusion Criteria	
	BC treated with aromatase inhibitors ± GnRH analogues (aGnRH)
	Menopause (natural or induced) and signs / symptoms of GSM; Vaginal pH ≥ 5
	Negative Human Papillomavirus (HPV) cytology and / or determination
	Intention or willingness to have sex
	Signed informed consent
Exclusion criteria	
	Vaginal hormonal treatment in the last 6 months
	Vaginal moisturizers and / or lubricants during the 30 days prior to study treatment
	Laser treatment, radiofrequency, hyaluronic acid, lipofilling in the vagina during the last 2 years
	Ospemifene treatment
	Being affected for: active infection of the genital tract; intraepithelial neoplasm of cervix, vagina, or vulva; have or have been treated for genital cancer; Genital prolapse stage \geq II.

ANNEXED:

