([https://www.maturitas.org/article/0378-5122\(95\)00956-6/pdf](https://www.maturitas.org/article/0378-5122(95)00956-6/pdf)). This index subjectively assesses the vagina's staticity, the amount of discharge, the integrity of the epithelium and humidity, along with pH as the only objective criterion. A score of ≤ 15 indicates AVV. It is the Index most used in publications reporting improvement of AVV with the use of lasers.

*²Vaginal vaginal pH: Using a pH test strip, colorimetric analysis of the pH of the vaginal discharge is performed.

*³Maturative Index: Using vaginal cytology, the percentage of parabasal, intermediate and superficial cells is calculated, allowing us to calculate the epithelial thickness indirectly.

*⁴ Visual Analog Scale (VAS): Evaluates 3 symptoms of AVV: dyspareunia, dryness and burning. Score from 0 to 10 (unbearable symptom). Symptoms are considered moderate from ≥ 4 .

*⁵ Female Sexual Function Index (FSFI): Generic sexual questionnaire validated for cancer survivors. We used the 19-item self-reported Spanish validated questionnaire to assess 6 sexual dimensions (desire, arousal, lubrication, orgasm, satisfaction and pain) and the global sexual function. Score ranges from 1,6 to 36, with the higher score indicating a better sexual Function. Function. A cut-off value of ≤ 26.55 indicates risk of sexual dysfunction, however, it could inflate female sexual dysfunction rates in those women whose sexual activity frequency is lower than once a month or in non-sexually active women. (<https://scielo.conicyt.cl/pdf/rchog/v69n2/art06.pdf>)

*⁶ Body Image Scale-Spanish version (S-BIS): Assesses 10 domains of body image in 10 questions and is applicable in patients with any type of cancer and different therapeutic regimens. The total score ranges from 0 to 30. The higher the score, the greater the concern regarding body image. (<https://www.ncbi.nlm.nih.gov/pubmed/25135839>).

[figure not shown]
*⁷ Quality of life Short Form 12 (SF-12): It consists of 12 items from the 8 dimensions of the SF-36 Physical Function (2), Social Function (1), Physical Role (2), Emotional Role (2), Mental health (2), Vitality (1), Body pain (1), General Health (1). (http://www.ser.es/wp-content/uploads/2015/03/SF12_CUESTIONARIO.pdf)

VVA: Severity classification / assessment Vaginal Health Index (Gloria Bachmann)

Score	1	2	3	4	5
Elasticity	none	poor	fair	good	excellent

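### The secondary outcome named resumption of sexual activity is coded as current status, so its result mixes resumption with continued activity and cannot support a statement about resumption.

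*Combined protocol and SAP*

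**What the plan says.** - **Outcome.** Under AIMS, the secondary sexual outcomes begin with "resumption sexual activity (sexually active vs non-sexually active"). No change from inactive to active is defined, and no denominator is given.
- **Who enters.** The only criterion on sexual activity in Table 1 is "Intention or willingness to have sex". STUDY SUBJECTS describes women who have symptoms "despite receiving first-line non-hormonal treatment: regular sexual activity", followed by moisturizers, lubricants and other measures. Active women are therefore recruited. Footnote 5 to Table 2 warns that the FSFI cut-off may overstate dysfunction when the frequency of activity is "lower than once a month or in non-sexually active women", so inactive women are expected too.
- **Analysis.** STATISTIC ANALYSIS sends repeated "binary or non-normal variables with marginal models (Generalized Estimating Equation: GEE") and makes intention to treat the main analysis. Adjustment for the baseline value appears only in the sentence on the MMRM.
- **Data.** Table 2 schedules the FSFI at T0, T6 and T12. FSFI items 3 to 14 each offer a response for no sexual activity in the past four weeks. A sexual anamnesis is taken at baseline.

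**The concern.** A woman who is already active at T0 cannot resume. She can only continue or stop. If she is counted in an outcome called resumption, her continued activity is scored as a success of the same kind as another woman's return to activity.

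Two misreadings could follow. A real effect on resumption could look small because part of the denominator was never able to resume. Conversely, a difference could be reported as resumption when it arises only because fewer active women stopped in one arm. The reported proportion would not let a reader tell these apart.

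**Working it through.** The plan gives no expected rate, effect or sample size for this outcome, so there is no figure of its own to reproduce. The 44 per arm in SAMPLE CALCULATION concerns the FSFI score.

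**Inputs from the documents:** 44 women per arm (88 in all) and 15% loss. The only activity rate is in BACKGROUND, from a cited study of a different cohort: "Only 52% of women had been sexually active when endocrine therapy began". Its complement, 48%, serves here as an illustrative inactive share.

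**Assumptions:** inactive share at T0 of 25% to 60%; resumption of 40% v 20% among inactive women; continuation among active women as stated at each step.

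**1. What the status contrast estimates.** Let i be the share inactive at T0, r the proportion of these who resume, and c the proportion of active women who continue. The proportion active at follow-up is i × r + (1 − i) × c. The difference between arms is therefore

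i × (difference in r) + (1 − i) × (difference in c).

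**2. Equal continuation in both arms.** Only the first term remains. For a true resumption difference of 20 points:

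| Inactive at T0 | All-women difference |
|---|---|
| 25% | 0.25 × 20 = 5 points |
| 48% | 0.48 × 20 = 9.6 points |
| 60% | 0.60 × 20 = 12 points |

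**3. No resumption effect, unequal continuation.** Take i = 0.48, resumption 20% in both arms, and continuation 95% v 80%.
- Arm with 95% continuation: 0.52 × 0.95 + 0.48 × 0.20 = 59.0%
- Arm with 80% continuation: 0.52 × 0.80 + 0.48 × 0.20 = 51.2%

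The status outcome differs by 7.8 points although resumption is identical.

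**4. Size of the at-risk set.** Evaluable women: 88 × 0.85 = 74.8. Inactive among them, if loss is unrelated to T0 status: 0.48 × 74.8 = 35.9, or about 36 (18 per arm). The range is 0.25 × 74.8 = 18.7 to 0.60 × 74.8 = 44.9.

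**5. Precision at 48% inactive (normal approximation).**
- Inactive women only, 40% v 20%, 18 per arm: SE = √(0.40 × 0.60/18 + 0.20 × 0.80/18) = 0.149. The 95% half-width is 1.96 × 0.149 = 29 points, around a difference of 20.
- All women, 95% continuation in both arms, 37 per arm: proportions 0.494 + 0.48 × 0.40 = 68.6% and 0.494 + 0.48 × 0.20 = 59.0%. SE = √(0.686 × 0.314/37 + 0.590 × 0.410/37) = 0.111. The half-width is 22 points, around a difference of 9.6.

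The restricted comparison has the wider interval but the larger signal relative to its error (20/14.9 = 1.3 against 9.6/11.1 = 0.9). Neither is precise.

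**The case against.** **The all-women denominator is inferred.** A reader might take it that the plan says resumption is analysed in every randomised woman. It does not. The inference rests on the intention-to-treat statement, the GEE rule for binary repeated variables and the absence of any subset. The section also allows Fisher's exact test for other variables, which could serve a single transition. This stands, and it is why the point is put as the natural reading. It does not remove the problem, since no reading in the text supplies an at-risk set.

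**Activity status is a legitimate outcome.** A reader might infer that the outcome fails its objective altogether. The documents do not support that. The heading above it is "MAIN GOAL: Report an improvement in sexuality", and the proportion active by randomised arm is a valid comparison that serves it. The defect is confined to calling that proportion resumption.

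**The inactive share is unknown.** A reader might conclude from the 52% that about half the women cannot resume. That figure describes another cohort at the start of endocrine therapy. This trial requires willingness to have sex and lists regular activity among current treatments, so its share may differ considerably. Hence the range.

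**Chance imbalance in T0 activity is not bias.** Under randomisation it is sampling error, which the interval covers. Adjustment for T0 status is worth having, but imbalance is no separate fault of the plan. Entering T0 as a repeated measure in the GEE would estimate change in prevalence, which is still not resumption.

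**A four-week FSFI rule alone would misclassify some women.** Those active less than once a month could be scored inactive at T0 and then counted as resuming when nothing had changed. This stands and is dealt with in the fix.

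**Conclusion.** The concern holds in a limited form. As coded, the outcome yields a valid comparison of activity status by arm but cannot support a statement about resumption, because it adds continued activity to it. With equal continuation, a 20-point resumption effect appears as 5 to 12 points if 25% to 60% of women are inactive at T0. With unequal continuation, a difference can appear with no resumption effect at all. The structural result needs no assumption beyond a mixed population. The sizes rest on assumed rates that the documents do not give.

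It would go too far to infer that the trial's main conclusion is at risk. This is one of many secondary outcomes, its place in the list implies no stated hierarchy, and the FSFI primary outcome and the sample size are unaffected. It is still more than missing detail, because following the stated coding would produce a mislabelled result.

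**What to change.** 1. Label the all-women outcome *sexually active at T6/T12*, and adjust its GEE for activity status at T0.
2. Define resumption as active at T6 or T12 among women inactive at T0. Compare it by arm, with the denominator shown and an interval given.
3. Report continued activity separately in women active at T0.
4. Derive T0 status from the FSFI no-activity responses together with the baseline sexual anamnesis. State in advance how to classify women who mark no activity on only some of items 3 to 14, and women active less than once a month.

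**Cost.** A revised definition and a few sentences of analysis text. The FSFI is already collected at T0, T6 and T12 and the anamnesis at baseline, so no new visit or form is needed. The downside is the small at-risk set: the resumption estimate will be imprecise and should be presented as an estimate with its interval, not as a test expected to be decisive.

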All eligible women will be informed about the study by briefing the participants on the study objectives and taking into account their willingness to participate (telematic visit). After an interval of at least 48h the patient will have a second visit (presential) and if she wants to participate the signed informed consent form will be checked. Both in- and exclusion criteria will be reviewed and if found suitable, the patient will be randomized. Both the patient information letter and informed consent form are attached as a separate document. Patients can leave the study at any time for any reason if they wish to do so without any consequences. The investigator can decide to withdraw a subject from

the study for urgent medical reasons. Patients who withdrew their informed consent will not be replaced. We will replace patients that are randomized by mistake, for example because of technical errors with online randomization. Patients withdrawn from the intervention but not from informed consent will be followed up.

None of the subjects will receive any (financial) compensation for participating in this trial. However, to minimize dropouts and build patient loyalty, we will offer them at the end of the study an additional laser treatment session, and those in the placebo group will be offered the 5 treatment sessions.

BUDGET:

Please give a detailed and itemized budget, see T&C for eligible and ineligible costs

Execution Expenses

A) Personnel costs

A postgraduate research student ([name]) will be hired 15h/week during 18months in order to perform task described in the Workplan. In addition, will be in charge of:

- Transcription of data to database.
- Management and coordination of patient appointments, as well as evaluation and resolution of problems derived from the study.
- Evaluation of results.
- Writing of manuscript.

B) Acquisition of materials and contracting of services

PH meter paper roll 5m x 2 IU x 10 = € 20

Maturation index (provided by Hospital Clinic de Barcelona): 12€ x 264 (88 patients throughout the study in 3 timepoints) = 3168€

Kit Silicone vaginal dilator (ref 69-4805-05-3) 44 units x 34,95 € (50% patients of the study) = 1537,8€

Vaginal vibrator (ref. 729232) x 88 units x € 8.95 =787,6€

Vaginal lubricant tube 100 mL x 616 IU x € 3,5 (for 88 patients throughout the study) = 2156€

Moisturizer hyaluronic acid-based ovules (Cerviron®) provided free of charge by Interpharm (for 88 patients throughout the study) = 0€

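### Read literally, fixed 1:1 blocks of 2 let one disclosed arm fix a second with certainty; undisclosed mixed blocks of 4 and 6 remove most certain deductions, though not the total information, at almost no cost

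*Combined protocol and SAP*

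**What the plan says.** The randomization plan is one sentence under METHODS, RANDOMIZATION PROCESS: "A randomization list will be generated in multiple blocks of 2 and 1: 1 ratio", made in Stata. One breast cancer unit recruits. No stratification factor, varying block size, list custodian or concealment procedure is given. The sample calculation asks for "44 subjects in the first group and 44 in the second".

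On blinding, STUDY GROUPS says "The control group will receive treatment with a sham-CO2 laser using a double-blinded protocol". The documents do not say which staff are blinded or who sets laser or sham.

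Three other places bear on the point:
- ETHICAL AND REGULATORY PERMISSIONS: "We will replace patients that are randomized by mistake, for example because of technical errors with online randomization". This is the only mention of an online system.
- The same section, on retention: "we will offer them at the end of the study an additional laser treatment session". Women in the placebo group are offered five sessions instead, so the offer differs by arm.
- The Vaginal Health Index note in Annex 1 describes a subjective assessment of several items, including "the integrity of the epithelium and humidity, along with pH as the only objective criterion".

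**The concern.** A 1:1 block of 2 can only be laser-sham or sham-laser. With one unstratified list, the women randomized 1st and 2nd, 3rd and 4th, and so on are in opposite arms by construction. The block size is printed in the protocol, so staff who read it have the key. If such a person learns one woman's arm and knows the randomization order, the partner's arm follows.

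What is at stake is the blinding of staff who score the Vaginal Health Index or record adverse events. For them, one known arm becomes two. Block size does not by itself unmask the woman who completes the FSFI.

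**Working it through.** **Inputs.** From the documents: 88 women, 44 per arm, 1:1, one list, blocks of 2 (literal reading). Assumed: sizes 4 and 6 equally likely, so 40% of women fall in blocks of 4 and 60% in blocks of 6; and a probability q that a woman's arm becomes known to the same staff, taken as 5%, 10% and 25%.

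**The plan's own figure.** The documents state no predictability figure. The 44 per arm matters here only for cost. The plan gives the error rates ("Accepting an alpha risk of 0.05 and a beta risk of less than 0.1 in a bilateral contrast") and an SD of 1 but no difference to detect, so 44 cannot be reproduced. Working backwards, it gives 90% power at about 0.70 SD (t-test, no dropout allowance).

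**1. One known arm.** In a block of 2k, any given block-mate is in the opposite arm with probability k/(2k-1): 1 for size 2, 2/3 for size 4, 3/5 for size 6.
- Pair partner (1-2, 3-4, ...), always in the same block because all sizes are even: 100% with blocks of 2; 0.4 x 2/3 + 0.6 x 3/5 = 62.7% with 4/6.
- Next woman, block boundaries unknown: with blocks of 2, 0.5 x 1 + 0.5 x 0.5 = 75%; with 4/6, 0.4(3/4 x 2/3 + 1/4 x 1/2) + 0.6(5/6 x 3/5 + 1/6 x 1/2) = 60%.

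**2. An arm only inferred, with accuracy a.** With blocks of 2 the partner is predicted with accuracy a. With 4/6 it is 0.5 + (2a-1) x 0.127. At a = 70%, 80%, 90% this gives 70%, 80%, 90% against about 55%, 58%, 60%.

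**3. Further women unmasked with certainty.** A woman not herself disclosed becomes certain when all k opposite-arm women in her block are disclosed. The 4/6 and 2/4/6 rows assume that staff know the block boundaries, which is unfavourable to those schemes.

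| Scheme | Formula | q = 5% | 10% | 25% |
|---|---|---|---|---|
| Blocks of 2 | 88q(1-q) | 4.2 | 7.9 | 16.5 |
| Mixed 4/6 | 88(1-q)(0.4q² + 0.6q³) | 0.1 | 0.4 | 2.3 |
| Mixed 2/4/6 | 88(1-q)(q/6 + q²/3 + q³/2) | 0.8 | 1.6 | 4.6 |

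If only half of the disclosures reach the same staff, replace q by q/2: blocks of 2 give 2.1, 4.2 and 9.6; mixed 4/6 gives 0.02, 0.09 and 0.57. At q = 0 every entry is 0.

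**4. Total information.** Summed over the 2k-1 block-mates, the excess of correct guesses over chance is k - (2k-1)/2 = 0.5 for every k. One isolated disclosure is worth half an extra correct guess at any block size.

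**5. All earlier arms known.** With blocks of 2, half of the assignments are certain and half are coin tosses: 75% best guess, 50% certain. With 4/6 and only the set of sizes known, simulation gives 69% best guess and about 5% certain.

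**6. Broken pairing.** If one list slot is unseen by staff, pairs before it stay intact (100%) and pairs after it straddle two blocks (50%). Averaged over a random position this is about 75%; simulation gave 74.7%.

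**7. Cost of mixed 4/6.** At 88, simulated lists differ by 2 women in about 22% of cases (22.4% of 20,000 lists) and are otherwise balanced. If recruitment stops at 85 or 87, a difference of 3 occurs in about 2% of lists. Relative efficiency is 4 x 43 x 45/88² = 0.9995 for 43/45 and 4 x 42 x 45/87² = 0.9988 for 42/45. At the difference that 44/44 detects with 90.00% power, 43/45 has 89.99%.

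**The case against.** The strongest reply is that larger blocks do not reduce what a disclosure reveals. Step 4 shows that this is correct: the information is spread over more women at lower confidence. If staff learn arms in sequence, the best guess falls only from 75% to 69%. What the change removes is most of the certainty. It would be too much to infer that it removes the predictability.

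Second, q is assumed. The only disclosure route in the documents is the differing offer of further laser, and it is weak. The text does not say whether the study's end means each woman's own end or that of the whole trial. An offer at her own end would follow her last listed rating at T12. It would also follow nearly all of her partner's ratings: if 88 women enter over 2 to 4 months, as the schedule suggests, entries lie on average 60/87 = 0.7 to 120/87 = 1.4 days apart. An offer at the end of the whole trial would follow all ratings. This limits the size of the point.

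Third, the sentence may mean block sizes that are multiples of 2, and replacement of women randomized by mistake could shift the pairs. Both are fair. Sizes 2, 4 and 6 leak less, but still leak in the blocks of 2; and one unseen slot leaves about 75%, well above chance.

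Fourth, whoever sets laser or sham knows the arms at any block size. If that person also rates outcomes, block size does not help with those ratings. This stands, and it confines the point to other staff.

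A reader might also infer biased enrolment or biased counselling. The documents describe no route by which recruiters would learn an arm before the next woman is randomized, and the listed PLISSIT assessment at T0 precedes session 1.

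**Conclusion.** The point holds as a minor, inexpensive improvement. On the literal reading, one known arm plus the randomization order makes a second arm certain. Mixed blocks of 4 and 6 remove most such certain deductions and leave the total information from an isolated disclosure unchanged. The counts in step 3 rest on the assumed q and on intact pairing, and they are zero if blinding holds.

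A reader might conclude that the primary result is at risk. The documents do not support that: the FSFI is self-reported, block size does not unmask the woman, and no bias in any outcome has been quantified. Nor do they show that blinding will fail. The benefit is confined to the staff-rated secondary outcomes and adverse event recording, and to staff who do not set laser or sham.

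**What to change.** Before the first randomization, replace the blocks of 2 with permuted blocks of randomly varying size 4 and 6. Withhold the sizes from enrolling, treating and assessing staff, and keep them out of the protocol that those staff read. If multiples of 2 were meant, correct the sentence and leave out size 2.

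The work is a change to the Stata list code and one or two sentences of text. The statistical price is the small imbalance in step 7: at most 0.05% of efficiency at 88 women, and 0.12% in the rare 42/45 case. The change cannot be made later for women already allocated.
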